#### 1 Introduction

# 1.1 Background

Chordomas are malignant tumors arising from embryonic notochord remnant. The majority of these tumors occur along the craniospinal axis: 50% grow in the sacrococcygeal regions, 35% in the base of the skull and 15% in the spine [1]; [2]. The incidence of chordoma is quite low. There is a slight male predominance in chordomas originating from the spinal cord, whereas lesions of the skull are seen more frequently in females. They have two age peaks of incidence, one in the fourth decade for skull lesions and one between the fifth and seventh decades for lesions that originate from the spinal cord and sacral region. Chondrosarcomas most commonly involve the femur with a striking predilection for the secondary ossification centers. Chondrosarcomas arising de novo present most commonly in the femur; and secondary chondrosarcomas are most prevalent in the ilium. They account for 10-20% of malignancy primary bone tumors. Age range is from 7 to 73 years with the most commons diagnosis between 30 and 60 years of age. Males predominate slightly in most series but mesenchymal chondrosarcoma occur more frequently in women. Conditions that predispose to chondrosarcoma include Ollier's disease, Paget's disease, Maffucci's syndrome, previous exposure to intravenous Thorotrast, chondromyxsoid fibroma and prior radiation therapy.

Chordomas have a slow growth and a tendency to destroy the bone locally. In their growth, they compress on adjacent tissues and structures, and this compression is responsible for most clinical symptoms. Although chordomas are essentially locally malignant tumors, they sometimes metastasize; the incidence of metastasis ranges from 10-25% [3]. They occur in the late phase of the disease or with a very large, massive primary lesion. Chondrosarcomas are locally aggressive lesion with a high propensity for local recurrence, which usually occurs within 5 years after treatment. Head and truncal chondrosarcomas have an 85% chance of recurring at the primary site. They usually follow a more indolent course. The most common site of distal metastases is the lungs, followed by bone, liver, kidney, breast and brain. Up to 10% of chondrosarcomas can dedifferentiate into aggressive fibrosarcomas or osteosarcomas.

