The five year survival rate for patients with chordomas is around 80% while for chondrosarcomas is 100% [4, 5]. The standard treatment of choice remains to be treated with aggressive surgery. The standard surgical procedure is a wide total excision. The biopsy tract must be excised, and the tumor should not be exposed during the operative procedure. The recurrent rate can vary from 15% with "adequate" surgery to 87% with inadequate procedures. Close follow up is needed, as these tumors can relapse 10 years or more from surgery. Most problems in treating patients with chordomas derive from the location of the tumor. The proximity of the tumor mass remains the preferred method of treatment for spinal and sacrococcygeal chordomas. Survival after radical surgery is normally long, although most patients experience a local failure in the course of the disease. The role of radiation is these tumors are not completely defined. However, data supports the efficacy of irradiation as adjuvant treatment after incomplete surgical resection. When surgery is not possible, radiation therapy can be used as a single-modality treatment. Different techniques and different types of ionizing radiation have been used to overcome dose-limitation problems. Based on current data, a combination of surgery and postoperative irradiation can be considered standard

treatment for resectable chordomas. If surgery is not indicated because of the location of the tumor, radiation therapy as a single modality can be considered a standard procedure for definitive treatment.

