### **3.4** Early Withdrawal of Subjects

### 3.4.1 When and How to Withdraw Subjects

- Recurrent or Progressive Disease: Subjects who have clinical or radiologic evidence of recurrent disease will undergo an evaluation to document the nature of the abnormality. If recurrent or progressive cancer is diagnosed, the subject will be considered off study at that time.
- PI Decision: Subjects may be withdrawn at any time during the study if the PI believes it is in the subject's best interest. In this event, the reasons for withdrawal will be documented.
- Subject Participation: Refusal to continue treatment, follow-up, comply with the protocol or withdrawal of consent. In this event, the reasons for withdrawal will be documented.
- Adverse Event (including intercurrent illness, unacceptable toxicity).

Once the subject has discontinued treatment, the primary reason for discontinuing treatment must be clearly documented in the subject's records and on the CRF. The investigator will assess each subject for response at the time of withdrawal.

Every effort will be made to follow all subjects off study for toxicity and survival unless patient withdraws consent. If subjects withdraw from the study at any time, we will ask for his/her written permission to continue to access medical records for overall survival. Acute toxicities will be assessed for 90 days from the first date of treatment. Survival will be followed for a minimum of 5 years.

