#### 7.1.2.2 Secondary Endpoints

Late toxicity is defined as any grade 3 or higher toxicity, considered probably or definitely related to radiation, observed later than 90 days from completion of therapy excluding cranial nerve palsies or nerve root symptoms as these may be due to the tumor itself or prior surgery. Late toxicities will be graded according to the CTCAE version 4.0. The time frame for late toxicity is open-ended and late toxicities have been known to occur a year or more after therapy. Follow-up for late toxicity will cease when a patient experiences disease progression, since 2nd line therapies may then be initiated.

Progression-free and overall survival are defined as the time from start of radiotherapy to first documented progression (local or distant event for PFS), death due to any cause or last patient contact alive. The local control rate (i.e., local progression only) may also be evaluated.

Fatigue will be scored by the Brief Fatigue Inventory (BFI), a validated instrument, which will be evaluated at the following time points: Pre-radiation, during treatment, at the inspection visit, and at approximately 3, 6, 9, 12 months post-radiation and then every 6 months for years 2 and 3, and yearly for year 4 and 5. It is expected that BFI score will increase (as fatigue worsens) in the first 6-12 months post-radiation and then the BFI score will decrease (as fatigue improves) at 12-24 months post-radiation.

Neurocognitive function will be assessed by the FACT-BR, which will be evaluated at preradiation, during treatment, at 3, 6, 9, 12 months post-radiation and then every 6 months.

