#### 7.2.4 Statistical Analyses.

Analyses of acute and late toxicity and fatigue will be completed within 1 year of completion of accrual. Time-to-event outcomes and long term longitudinal measurements of fatigue and neurocognitive function will be analyzed 2-3 years after completion of accrual. Descriptive analyses and subset analyses are likely. The purpose of these subset analyses is hypothesis generation. Subgroup analyses will likely describe time-to-event outcomes by histology (e.g., chordoma or chondrosarcoma) and extent of surgery (e.g., biopsy only, partial debulking, and maximal debulking). They will produce estimates of clinical outcomes, to aid in the design of future clinical trials.

Acute and Late Toxicity. All acute and late toxicities will be graded by CTCAE Version 4.0 and tabulated. Toxicity rates and 95% confidence intervals will be calculated. The maximum half-width of the 95% confidence interval is  $\pm 14\%$  based on 50 patients.

Time-to-Event Outcomes. Trials of chordomas and chondrosarcomas which combine proton with photon, have demonstrated 5-year progression-free survival rates (i.e., free of local failure) of 60-80%. We do not expect the 5-year PFS rate to be much different with protons. Progression-free and overall survival and time to local failure, will be estimated by the Kaplan-Meier method. Median and 5-year estimates and 95% confidence intervals will be calculated.

Fatigue (Brief Fatigue Inventory, BFI) & Neurocognitive function (FACT-Br) will be summarized by mean and standard deviation calculated and plotted over time. We will examine the plots for the expected worsening of function in the 6-12 months post-radiation and gradual improvement from 12-24 months. Pre- and post-treatment comparisons at a primary time point (e.g., at 24 months post-radiation when function should have recovered) will be evaluated by Student's paired t-test or nonparametric Wilcoxon signed ranks test. A general strategy to assess trends over time in longitudinal data is to employ linear mixed effects models, which can account for the impact of covariates such as anti-seizure medication and baseline performance status. The BFI can also be categorized as mild (1-3), moderate (4-6) and severe (7-10). The rates of patients in the severe category will be estimated at each time point. Of primary interest are the rates at 12 and 24 months post-treatment.

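### Kaplan-Meier for time to local failure censors deaths without local failure, so it modestly overstates the proportion who fail locally; cumulative incidence would not

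*Combined protocol and SAP*

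**What the plan says.** Section 7.2.4 (Time-to-Event Outcomes) uses one estimator for three endpoints: PFS, OS and "time to local failure, will be estimated by the Kaplan-Meier method". It adds that "Median and 5-year estimates and 95% confidence intervals will be calculated".

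The endpoints differ in what counts as an event. Section 7.1.2.2 runs PFS and OS to "first documented progression (local or distant event for PFS), death due to any cause or last patient contact alive", so death is an event for both. For the local endpoint it says only: "The local control rate (i.e., local progression only) may also be evaluated". Section 6.1.2 defines local failure by imaging and gives no censoring or competing-event rule.

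Under section 3.4.1, once recurrence or progression is diagnosed, "the subject will be considered off study at that time". Follow-up off study is then named for toxicity and survival, not for local status.

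**The concern.** Kaplan-Meier suits PFS and OS, because death ends both as an event. Time to local failure is different. A patient who dies without local failure can no longer have one, yet Kaplan-Meier treats that patient as censored and still liable to fail later. Read as the share of patients who fail locally, 1−KM is then too high.

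Local control is a listed secondary objective. Section 7.2.4 intends to describe time-to-event outcomes by histology and to use the estimates in designing later trials. On the document's own survival figures, deaths fall mainly on chordoma, so the excess would be uneven across the two histologies being described.

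**Working it through.** **Plan's own figures.** No sample size, event count or precision is stated for local failure. The nearest figure is the ±14% maximum half-width for toxicity rates with 50 patients. It reproduces: 1.96 × √(0.5 × 0.5/50) = 13.9%.

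**Inputs.**
- Five-year freedom from local failure, LC: 60-80% (section 7.2.4).
- Five-year survival: section 1.1 says that "The five year survival rate for patients with chordomas is around 80" per cent, and gives 100% for chondrosarcoma.
- Net 5-year risk of death without local failure, C: not in the documents. **Assumed** at 5%, 10% and 20%. The 20% case applies the whole chordoma death rate (100 − 80) to patients free of local failure.

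**Formula** (constant hazards). With a = −ln(LC) and b = −ln(1 − C):
- 1−KM = 1 − LC
- cumulative incidence = a/(a + b) × [1 − LC × (1 − C)]

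Example, LC 70% and C 10%: a = 0.3567, b = 0.1054, a/(a + b) = 0.772, and 1 − 0.70 × 0.90 = 0.370. Cumulative incidence = 0.772 × 0.370 = 28.6%, against 30.0% by 1−KM.

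| LC | 1−KM | C = 5% (excess) | C = 10% (excess) | C = 20% (excess) |
|---|---|---|---|---|
| 60% | 40.0% | 39.1% (0.9) | 38.1% (1.9) | 36.2% (3.8) |
| 70% | 30.0% | 29.3% (0.7) | 28.6% (1.4) | 27.1% (2.9) |
| 80% | 20.0% | 19.5% (0.5) | 19.0% (1.0) | 18.0% (2.0) |

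At C = 0, which the chondrosarcoma survival figure suggests, the two agree. A simulation of 50 patients (4-year accrual, analysis 3 years later, 4,000 runs) gave 30.1% against 27.2% for LC 70%, C 20%, and 20.2% against 19.2% for LC 80%, C 10%.

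**How firm the 20% case is.** It is a ceiling if patients without local failure die no faster than chordoma patients overall. At LC 60% it means 0.2231/0.7340 × 0.52 = 15.8% of patients actually die first. For a full 20% to die first, C would have to be about 25% and the excess about 4.9 points, but then nobody could die within 5 years after a local failure.

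**Precision.** With no censoring, the half-width is 1.96 × √(0.6 × 0.4/50) = 13.6 points at LC 60% and 1.96 × √(0.8 × 0.2/50) = 11.1 at LC 80%. In the two simulated settings, the spread of 1−KM (standard deviation 7.6 and 6.2 points) gives about 15 and 12 points.

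**Distant progression.** It does not prevent local failure, so it was checked separately. Assume 5-year net risks of 30% local failure, 5% death, and 10% or 20% distant progression. Let a, d and m be the yearly hazards of local failure, death and distant progression, and let the local hazard after distant progression be k × a.
- Local failure as first event = a/(a + d + m) × [1 − 0.70 × 0.95 × (1 − 0.10 or 0.20)] = 27.9% or 26.4%.
- Add failures after distant progression: ∫₀⁵ m e^(−(a+d+m)s) × ka/(ka + d) × [1 − e^(−(ka+d)(5−s))] ds.
- Total with k = 1: 29.3% in both cases. Total with k = 2: 30.4% or 31.5%.

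Kaplan-Meier, censoring at death and distant progression, gives 30.0% throughout. It is slightly high when k = 1 and too low when k = 2.

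**The case against.** The strongest objection concerns distant progression. A reader might infer that Kaplan-Meier overstates local failure there too, and that the fix is to count it as a competing event. The documents do not support this. Distant progression leaves local failure possible, and section 1.1 links chordoma metastasis to late or very bulky disease, where local risk may be higher; the check above shows that the direction can reverse. Counting it as competing estimates a smaller quantity, local failure as first event. The off-study rule is a gap in local-status data that no estimator fills. This stands, and the point is limited to death.

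A reader might also take the excess to be 1-5 points, using the statement that "the incidence of metastasis ranges from 10-25" per cent. That figure has no time horizon, concerns chordoma only, and counts metastases that follow local failure as well as those that precede it. Section 1.1 also says that most patients have a local failure at some stage after radical surgery, so many deaths would follow local failure and not compete with it. This stands too.

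Third, Kaplan-Meier local control is a recognised summary, the plan does not say that 1−KM will be read as the proportion failing, the censoring rule is implied and not written out, and the endpoint is secondary and descriptive. All true. They limit the importance, but they do not make Kaplan-Meier the right estimate of how many patients fail locally.

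**Conclusion.** The point holds for death without local failure. Its direction is certain wherever such deaths occur and 1−KM is read as the proportion failing. Under constant hazards and 60-80% local control, the excess is 0.5-0.9 points at an assumed 5% risk, 1.0-1.9 at 10%, and at most 2.0-3.8 for chordoma if the whole quoted death rate applied to patients without local failure. It is near zero for chondrosarcoma, and a pooled figure lies between.

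This is a minor improvement. The excess is well inside the confidence interval with 50 patients, and no test, threshold, stopping rule or sample size uses the endpoint. Whether censoring at distant progression biases the estimate up or down cannot be settled from the documents.

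**What to change.** In section 7.2.4, report the cumulative incidence of local failure by the Aalen-Johansen estimator, with death without local failure as the competing event, overall and by histology, with 95% confidence intervals. Write out the event, the competing event and the censoring rule. Keep Kaplan-Meier for PFS and OS, and optionally show the Kaplan-Meier local-control curve beside the new one.

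For distant progression, choose one rule and state it:
- record local status from available records after distant progression, so that death remains the only competing event; or
- treat distant progression as competing and label the result *local failure as first event*.

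The cost is a few sentences and a standard routine. Dates of death and distant progression are already needed for PFS and OS; only the first rule asks for extra data. The downside is a slightly less direct comparison with earlier series if those used Kaplan-Meier, which the documents do not say; the optional curve covers that case.

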#### **Secondary Objectives**

To assess acute side effects from irradiation using proton beam therapy for the treatment of chordomas or chondrosarcomas.

To assess late complications from irradiation using proton beam therapy for the treatment of chordomas or chondrosarcomas.

To compare the dose distribution to tumor and surrounding normal structures using DVH's (Dose Volume Histograms) generated from the proton plan used to treat the patient and the photon plan generated for comparison purposes.

To monitor the rates of local control as well as overall and disease specific survival using proton radiotherapy.

Version: 04/04/2014

To evaluate the time to progression and progression free survival of chordomas or chondrosarcomas treated with protons.

To evaluate the effect of proton beam radiation on neurocognitive outcome in patients with chordomas or chondrosarcomas.

To evaluate the quality of life (e.g., fatigue) in patients treated for chordomas or chondrosarcomas.

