#### 3.1 Inclusion Criteria

- Histologically confirmed diagnosis of chordoma or chondrosarcoma.
- Patients must have no evidence of metastatic disease based on routine imaging (Chest x-ray, CT or MRI of the chest/abdomen/pelvis, bone scan, etc).
- Patients must have an ECOG score equal to or less than 2.
- Age  $\geq$  18.
- Patients must be able to provide informed consent.
- Women of child-bearing potential as long as she agrees to use a recognized method of birth control (e.g. oral contraceptive, IUD, condoms or other barrier methods etc.). Hysterectomy or menopause must be clinically documented.
- Tumors arising in the skull and spine.

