CNS (BOS): spinal cord, brainstem, optic nerve (right/left), optic chiasm, eye (right/left), lens (right/left), cochlea (right/left), right and left hippocampus, pituitary, cerebellum, temporal lobes.

*Head and neck (Cervical spine):* salivary glands (parotid-right/left, submandibular right/left), larynx, oral cavity, upper esophagus, mandible, lungs, brachial plexus.

Spine (Thoracic/Lumbosacral): spinal cord, thecal sac.

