# **6.0 Study Procedures**

Patients will complete the Brief Fatigue Inventory and Fact Br which is specific to patients with CNS tumors. Fatigue and neurocognitive testing for these patients will continue for 3 years post radiation.

	Eligibility/ Pre- treatment	Weekly during treatment	1.1	O Follow-Up  X Months (approximat ely from completion of treatment) 3,6,9,12,15, 18, 21, 24 (approx.)	Months 30, 36 (approximatel y from completion of treatment)	1
Tests and						
Observations						
History and PE	X			X	X	X
ECOG Score	X		X	X	X	
CT/MRI	X			X	X	X

CXR	$X^3$					
Pathology	X					
Pregnancy Test	$X^1$					
Toxicity	X	X	X	X	X	X
Assessment						
Tumor	$X^2$			$X^2$	$X^2$	$X^2$
Measurement						
BFI (fatigue)	X	X	X	X	X	X
Fact Br (neurocog)	X	X	X	X	X	X

 $X^{I} A \text{ pregnancy test will be required for females of child bearing potential within 5 days of tx)}$ 

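### FACT-Br is summarised and tested over skull and spine patients together, so the neurocognitive result mixes patients with and without expected brain dose

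*Combined protocol and SAP*

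**What the plan says.** Section 2 sets one neurocognitive objective for the whole trial: "To evaluate the effect of proton beam radiation on neurocognitive outcome in patients with chordomas or chondrosarcomas". Section 3.1 admits "Tumors arising in the skull and spine". Section 6.0 collects the instrument without restriction by site: "Patients will complete the Brief Fatigue Inventory and Fact Br which is specific to patients with CNS tumors". Section 6.1 repeats it at each follow-up visit, and Section 7.1.2.2 makes FACT-Br the measure of neurocognitive function.

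The site-specific contouring list in Section 4.3.2 separates the groups anatomically. For base of skull it includes "right and left hippocampus, pituitary, cerebellum, temporal lobes". For thoracic and lumbosacral spine the whole entry is "spinal cord, thecal sac".

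For phase II, Section 7.2.4 says that BFI and FACT-Br "will be summarized by mean and standard deviation calculated and plotted over time". It adds that the change from before to after treatment at a main time point, 24 months being the example, "will be evaluated by Student's paired t-test or nonparametric Wilcoxon signed ranks test". Mixed models are described as a general strategy, with anti-seizure drugs and baseline performance status as example covariates. The subgroups it names are tumour type and extent of resection, and they are attached to time-to-event outcomes. Site appears in none of these places for FACT-Br.

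**The concern.** The objective asks what proton treatment does to cognition. The route by which it could do so is dose to the brain. The plan recognises this for skull-base tumours: Section 1.1 names temporal lobe and brainstem injury among the documented effects, and Section 4.5.2 limits dose to the temporal lobes and cerebellum. On the plan's own contouring list, that route is not expected in thoracic and lumbosacral patients.

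An all-patient mean therefore averages over two exposures. It estimates the effect in neither group, and its value moves with the proportion of spine patients who happen to enrol. Section 7.3 sets no target for spine patients, and no section gives a site mix for phase II. That weakens the stated purpose of providing estimates for the design of later trials. The plan already separates base of skull from spine when it judges feasibility (Sections 2, 7.1.4 and 7.3). It does not carry the distinction over to the endpoint where it bears most directly on interpretation.

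**Working it through.** **The plan's own figure.** No power, effect size or standard deviation is stated for FACT-Br, so there is nothing to reproduce for this endpoint. The only power figure, in Section 7.3, concerns severe fatigue on the BFI: 33% against 50%, n = 50, one-sided 5%. It reproduces: Φ[(0.17 − 1.645 × √(0.25/50)) / √(0.33 × 0.67/50)] = Φ(0.81) = 0.79, matching the stated 79%. It says nothing about FACT-Br.

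**Dilution of the mean.** Let p be the base-of-skull share, Δ the mean change in base-of-skull patients and s the mean change in spine patients.

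Pooled change = pΔ + (1 − p)s

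The only mix in the plan is 12 base-of-skull and up to 5 spine patients (Sections 7.1.4 and 7.3), so p = 12/17 = 0.706 and 1 − p = 0.294.

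- s = 0: pooled change = 0.706Δ, about 71% of the skull-base change.
- s = 0.5Δ: 0.706Δ + 0.147Δ = 0.853Δ.
- s = −0.5Δ: 0.706Δ − 0.147Δ = 0.559Δ.

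The documents give no value for s; these three values are illustrative.

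**Does restriction lose more through the smaller n than it gains?** Assumptions, none given in the plan: a standardised change of d = 0.5 in base-of-skull patients, zero change in spine patients, 50 patients with 24-month data, and a two-sided 5% paired t-test. With spine share f, the pooled mean is (1 − f)d and the pooled standard deviation is √(1 + f(1 − f)d²). At f = 5/17 these are 0.353 and 1.026, a pooled standardised change of 0.344.

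| Spine share | Pooled change as % of skull-base change | Power, pooled (n = 50) | Power, skull base only (n) |
|---|---|---|---|
| 10% | 90% | 87% | 91% (45) |
| 20% | 80% | 78% | 87% (40) |
| 29% (5/17) | 71% | 67% | 82% (35) |
| 50% | 50% | 39% | 67% (25) |

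At the 29% share, pooled against skull-base-only power is 31% against 41% for d = 0.3, 49% against 63% for d = 0.4, and 81% against 93% for d = 0.6.

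Under zero change in spine patients, restriction gains power at every mix tried. The reverse also needs stating: if spine patients changed exactly as much as skull-base patients, pooling would be better (93% with 50 patients against 82% with 35, at d = 0.5).

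**The case against.** **The plan leaves room for a site analysis.** Section 7.2.4 expects subset analyses, and its covariates are offered as examples. That is correct: the word pooled does not appear, and the reading rests on the absence of any site stratum. But permission is not commitment. The only analyses specified for FACT-Br would run over everyone, and site is known for every patient because the feasibility definition needs it.

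**The size is uncertain.** This stands. The 12/17 figure covers only the post-amendment feasibility cohort. It counts all spine levels, while the anatomical argument is clearest for thoracic and lumbosacral patients. The contouring list names no brain structure for cervical spine either, but incidental brain dose there is not excluded. Five spine patients is the upper end of what was anticipated; with a 10% share the power difference is only 87% against 91%.

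**A reader might infer a far larger dilution** from Section 1.1, which reports that "50% grow in the sacrococcygeal regions, 35% in the base of the skull and 15% in the spine", and conclude that only about a third of the skull-base effect would survive. The documents do not support that. The figure describes chordomas in general, omits chondrosarcoma, which is also eligible, and is not a forecast of enrolment. The trial's target is base-of-skull patients, and Section 3.3 recruits partly through neurosurgery and otorhinolaryngology practices.

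**A reader might also infer that pooling always pulls the result towards no change**, or that the trial is set to declare cognition preserved. Neither follows. Spine patients' scores may move for reasons other than brain dose, which could bias the pooled mean either way. No section ties a claim or decision rule to FACT-Br.

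**Extending the point** to the BFI models, or to whether FACT-Br deserves a neurocognitive label, is not supported: nothing in the documents shows a site problem for fatigue, and what the instrument measures cannot be settled from them.

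**Conclusion.** The point holds as an improvement to a secondary, descriptive analysis. As written, Section 7.2.4 answers the neurocognitive objective with one mean and one paired test over patients with and without expected brain dose, so the answer depends on an unstated site mix.

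If spine patients do not change, the pooled change is about 71% of the skull-base change at the only mix the plan gives, and closer to 100% if fewer spine patients enrol. The power comparison of about 67% pooled against 82% for skull base alone rests on that same assumption, on d = 0.5, on complete 24-month data and on a two-sided 5% test. It shows that the smaller sample is not by itself a reason to pool; it does not predict the trial's power. The primary endpoint is not affected.

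**What to change.** In Section 7.2.4:

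- Report FACT-Br means and standard deviations over time, and the 24-month paired comparison, separately for base-of-skull and spine patients.
- State that the conclusion on the neurocognitive objective rests on the base-of-skull group.
- Include tumour site and a site-by-time term in the FACT-Br mixed model.
- Keep the all-patient summary, if wanted, as supportive, and give the number of patients per site beside it.

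This is a change of wording. It needs no new visits, questionnaires or patients.

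The cost is precision. With 35 patients instead of 50 and the same standard deviation, the skull-base interval is about √(50/35) = 1.20 times as wide. The spine estimate will be very imprecise, with about five such patients anticipated in the feasibility cohort, and should be presented as descriptive only.

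### The 24-month before/after comparison of BFI and FACT-Br uses only patients with both scores, and the plan does not settle whether patients who progress are still scored

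*Combined protocol and SAP*

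**What the plan says.** Section 7.2.4 summarises BFI and FACT-Br by mean and standard deviation and plots them over time. The comparison of pre- and post-treatment scores at a primary time point "will be evaluated by Student's paired t-test or nonparametric Wilcoxon signed ranks test". The time point is given as an example: "at 24 months post-radiation when function should have recovered". The next sentence adds: "A general strategy to assess trends over time in longitudinal data is to employ linear mixed effects models". That model is not assigned to the 24-month comparison. The section gives no rule for scores missing through progression, death or dropout, and no sensitivity analysis.

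Two sections bear on who will have a 24-month score, and they do not agree:

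- Section 3.4.1: "If recurrent or progressive cancer is diagnosed, the subject will be considered off study at that time". It then says: "Every effort will be made to follow all subjects off study for toxicity and survival unless patient withdraws consent". BFI and FACT-Br are not named.
- Section 6.0: "Fatigue and neurocognitive testing for these patients will continue for 3 years post radiation". No exception is made for patients who progress.

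Section 7.1.2.2 also says: "Follow-up for late toxicity will cease when a patient experiences disease progression".

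**The concern.** A paired t-test or signed-rank test drops anyone without both scores. If scoring stops at progression, the 24-month comparison is made in patients who are alive, progression-free and still reporting. It is then read as evidence on whether function has recovered.

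Section 1.1 says chordomas compress neighbouring structures and that this causes most symptoms, so it is plausible that patients who progress worsen more from baseline. In that case the paired result would lean towards recovery. It would also use none of the scores recorded between baseline and 24 months, including those of patients who later progress.

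This matters because Section 7.2.1 expects protons to reduce fatigue and toxicity, and makes the summary of fatigue scores a purpose of phase II.

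**Working it through.** **The plan's own fatigue figure.** The only power statement for fatigue is in Section 7.3: 79% for the 12-month severe-fatigue rate, 33% against 50%, N = 50, one-sided 5%. It reproduces: Φ((0.17 − 1.645·√(0.25/50)) / √(0.33·0.67/50)) = Φ((0.170 − 0.116)/0.0665) = 0.79. That is a separate analysis. No power is given for the 24-month paired comparison.

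**Inputs**
- N = 50 (Section 7.3).
- 5-year PFS of 60-80%, not expected to differ much with protons (Section 7.2.4).
- PFS runs from the start of radiotherapy (Section 7.1.2.2), and treatment takes up to about 9 weeks (Section 4.6). So 24 months after radiotherapy is about 26 months on the PFS clock.
- The shape of the PFS curve is not given, so two assumptions are used.

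**Constant hazard (assumption).** S(26) = S(60)^(26/60).

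**Rising hazard (assumption).** The stereotactic radiotherapy series in Section 1.1 reports local relapse-free survival of 82% at 2 years and 50% at 5 years. A constant hazard through 50% would give 0.5^0.4 = 76% at 2 years, so that curve falls more slowly early on. The Weibull shape through both points is k = ln(ln 0.82 / ln 0.50) / ln(24/60) = 1.365, so S(26) = S(60)^((26/60)^1.365) = S(60)^0.319.

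**Possible bias.** Let f be the share without a 24-month score and D the amount by which their mean change is worse. The all-patient mean change equals the completer mean plus f·D, so the completer mean is too favourable by f·D. D = 2 BFI points is an assumption; the documents give no scores by progression status.

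| Hazard | 5-year PFS | S(26) | Progressed or died, of 50 | Remaining | f·D at D = 2 |
|---|---|---|---|---|---|
| Constant | 60% | 0.801 | 9.9 | 40.1 | 0.40 |
| Constant | 80% | 0.908 | 4.6 | 45.4 | 0.18 |
| Rising | 60% | 0.849 | 7.5 | 42.5 | 0.30 |
| Rising | 80% | 0.931 | 3.4 | 46.6 | 0.14 |

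The range is about 3 to 10 patients and 0.1 to 0.4 points on a 10-point scale. Ordinary dropout would add to the loss. So might distant progression and death, because Section 7.2.4 glosses its 60-80% as freedom from local failure. The shift scales with D: at D = 0 there is none, and at D = 1 it is half the figures shown.

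**The case against.** Several points on the other side have force.

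- **Scores may not be missing.** A reader might infer that progressing patients have no 24-month score by design. The documents do not support that. Section 6.0 continues testing for 3 years without exception, and Section 3.4.1 does not say that the questionnaires stop. What stands is that the two sections leave it open.
- **The fatigue test is elsewhere.** A reader might infer that this undermines the plan's test of whether protons reduce fatigue. It does not. The formal, though exploratory, test is the 12-month severe-fatigue rate. The paired comparison is secondary and unpowered, and a before/after change in a single arm cannot show an advantage over photons whatever the dropout.
- **The plan does not ignore the repeated scores.** It plots them and names mixed models. What is missing is the link between that model and the 24-month contrast.
- **More fatigued is not enough.** The test uses change from baseline. If patients who progress were equally more fatigued at baseline, no bias would follow.
- **Change while progression-free is a coherent target.** Section 7.1.2.2 stops late-toxicity follow-up at progression because second-line therapy may begin, and the same reasoning could apply to fatigue. For that target, leaving out progressed patients is not a bias. The plan does not state it.
- **A mixed model is not a cure.** A reader might infer that it would remove the 0.1 to 0.4 points. It removes only what earlier scores predict, under missing at random.

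**Conclusion.** The point holds as a minor improvement. The plan assigns the 24-month comparison to a test restricted to patients with both scores, has no rule for missing scores, and is unclear on whether scoring continues after progression. On the plan's own PFS range, about 3 to 10 of 50 patients could be affected, under either assumed hazard shape and before other dropout.

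The direction of any bias depends on whether those patients change for the worse relative to the rest. That is plausible but undocumented. The 0.1 to 0.4 BFI points rest on an assumed 2-point gap, and no corresponding figure can be given for FACT-Br. The consequence is for how a secondary single-arm result is read. It does not affect error control of a primary test, and it is not a criticism of the 12-month severe-fatigue test.

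**What to change.** 1. Reconcile Sections 3.4.1 and 6.0, so that it is clear whether BFI and FACT-Br are collected after progression. State how progression and death enter the 24-month comparison.
2. Estimate the baseline-to-24-month contrast for BFI and FACT-Br from the linear mixed model already named. Treat time as a categorical factor, because the plan expects worsening and then recovery. Use the baseline and the scheduled post-treatment visits, not the weekly on-treatment scores, and state the covariance structure in advance.
3. List the visits. The Section 6.0 table includes 15 and 21 months, while Section 7.1.2.2 goes to 6-monthly scoring after 12 months. Baseline plus the visits common to both up to 24 months (3, 6, 9, 12, 18, 24) makes 7 occasions, or 7·8/2 = 28 parameters if the covariance is unstructured. Adding the weekly scores would bring it to about 20 occasions and 20·21/2 = 210 parameters, too many for 50 patients.
4. Keep the paired t-test or Wilcoxon test as a sensitivity analysis. Report the number of pairs and the reasons for missing scores.

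The cost is analysis-plan wording and some modelling work, with no new visits unless the reconciliation adds scoring after progression. The price is a missing-at-random assumption: worsening that appears only after progression, and is never scored, is not recovered.
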